## **8.3 Compliance with clinical investigation intervention**

Due to the fact that at least one research employee will be present during the Game Ready applications and the measurements, the compliance of the study participants can be classified as high. No additional measures are taken to improve compliance.

## **8.4 Data Collection and Follow-up for withdrawn subjects**

The medical follow-up of subjects who drop out of the examination prematurely is described in chapters 9.2.5 and 9.2.6. There is no disadvantage for the participants if they discontinue their participation in the study and no further interventions are necessary for follow-up treatment.

## **8.5 Clinical investigation specific preventive measures**

Furthermore, any injuries and illnesses were defined as an exclusion criterion in order not to take the risk of intervention. The questionnaire also asks about any diseases and influences that preclude participation in the study. If there are doubts that are not medically proven, the study leader reserves the right to have them checked and thus exclude a test subject from participation.

## **8.6 Concomitant Interventions (treatments)**

No interventions will be carried out in the study other than those described in Chapter 8.1. Therefore, no further side effects are expected from participation in the study.

## **8.7 Medical Device Accountability**

The trials are taking place exclusively at the Regional Hospital Surselva AG, [name]. This means that there is no transport of the products and measuring instruments used. There is therefore no liability for the transport of the product.

[figure not shown]
## **8.8 Return, Analysis or Destruction of the Medical Device**

The Game Ready GR PRO 2.1 will be returned to MTR at the end of the measurement period. In the event of product defects, including malfunctions, usability issues, or insufficient information from the manufacturer, including labeling, the products will be returned to the sponsor for analysis.

**SUPSI**

## 9. CLINICAL INVESTIGATION ASSESSMENTS

# Procedure Game Ready - Study

# SUPSI

## 9.1 Clinical investigation flow chart(s) / table of clinical investigation procedures and assessments

The test subject information is sent to the test subjects' homes in advance or given in person during the orthopaedic consultation. All rounds take place on the premises of the Regional Hospital Surselva AG.

### 1. *Subject Information & Informed Consent Meeting*

30 min (questions and ambiguities will be discussed individually here)

### 2. *Running the Test Log*

Test log	
Cooling group	Control group
Visit 1: Screening and baseline preoperatively: information, written consent, examination of /Exclusion criteria, health questionnaire Physical Function [Score] Joint circumference [mm] Range of motion [degrees] Skin temperature [°C] Visual Analog Pain Scale [cm] 10-meter walk test [sec] Timed-up-and-Go [sec]	Visit 1: Preoperative screening and baseline information, written consent, examination of /Exclusion criteria, health questionnaire Physical Function [Score] Joint circumference [mm] Range of motion [degrees] Skin temperature [°C] Visual Analog Pain Scale [cm] 10-meter walk test [sec] Timed-up-and-Go [sec]
Daily cooling intervention In addition to the usual physiotherapeutic treatment: Daily Cooling and compression. One detailed treatment description can be found in chap. 8.1.1.	Daily Control Intervention In addition to the usual physiotherapeutic Treatment: No refrigeration (see chapter 8)
Visit 4: Follow up 4th postoperative day Physical Function [Score] Joint circumference [mm] Range of motion [degrees] Skin temperature [°C] Visual Analog Pain Scale [cm] Patient satisfaction [cm] 10-meter walk test [sec] Timed-up-and-Go [sec]	Visit 4: Follow up 4th postoperative day Physical Function [Score] Joint circumference [mm] Range of motion [degrees] Skin temperature [°C] Visual Analog Pain Scale [cm] 10-meter walk test [sec] Timed-up-and-Go [sec]

Visit 5: Follow up 6 weeks postoperatively
 
Physical function [Score] Joint circumference [mm]
 
Range of motion [degrees]
 
Skin temperature [°C]
 
Visual Analog Pain Scale [cm]
	
Visit 5: Follow up 6 weeks postoperatively
 
Physical function [Score] Joint circumference [mm]
 
Range of motion [degrees]
 
Skin temperature [°C]
 
Visual Analog Pain Scale [cm]

10-meter walk test [sec]
 
Timed-up-and-Go [sec]
 
Length of stay [days]
 
Morphine consumption [number]
	
10-meter walk test [sec]
 
Timed-up-and-Go [sec]
 
Length of stay [days]
 
Morphine consumption [number]

Test log	
Rounds	Time exposure

Visit 1: Screening and baseline preoperatively: information, written consent, examination of /Exclusion criteria, health questionnaire
 
Physical Function [Score]
 
Joint circumference [mm]
 
Range of motion [degrees]
 
Skin temperature [°C]
 
Visual Analog Pain Scale [cm]
 
10-meter walk test [sec]
 
Timed-up-and-Go [sec]
	60 min

Daily cooling intervention
 
In addition to the usual physiotherapeutic treatment: Daily Cooling and compression. One detailed treatment description can be found in chap. 8.1.1.
	
2x daily one treatment of 60 min = 120 min per day
 
4x 120 min per day = 480 min per stay

Visit 2: Follow up 4th postoperative day
 
Physical Function [Score]
 
Joint circumference [mm]
 
Range of motion [degrees]
 
Skin temperature [°C]
 
Visual Analog Pain Scale [cm]
 
Patient satisfaction [cm]
 
10-meter walk test [sec]
 
Timed-up-and-Go [sec]
	30 min

Visit 3: Follow up 6 weeks postoperatively  Physical Function [Score] Joint circumference [mm] Range of motion [degrees] Skin temperature [°C] Visual Analog Pain Scale [cm] 10-meter walk test [sec] Timed-up-and-Go [sec] Length of stay [days] Morphine consumption [number]	40 min
Total time commitment:	610 min

Any adverse events must be recorded during each visit. These possible time expenditures are not included in the test protocol.

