### 3. BACKGROUND AND RATIONALE

#### 3.1 Background and Rationale for the clinical investigation

Recovery after surgery is characterized by pain, swelling, and inflammation in the perioperative tissues. This also applies after total knee endoprosthesis (TKA). Due to the high concentration of nerve endings, the amount of bone resection and bleeding in a closed space (joint capsule), pain, swelling and inflammation are promoted. These factors can complicate the prescribed postoperative physical therapy program for mobilization. Consequently, the patient's functional abilities are compromised with postoperative pain, swelling, and inflammation and can affect the final outcome. Compression and cryotherapy have traditionally been used in the postoperative treatment of TKA to mitigate these factors. Compression is believed to reduce edema by increasing hydrostatic pressure, thereby promoting the outflow of fluid into the interstitial space. Cold therapy can reduce leukocyte migration and slow down the transmission of nerve signals, resulting in a reduction in inflammation and having a short-term analgesic effect (Su et al. 2012).

One study showed similar effects of cold compression bandages in simple arthroscopy, anterior cruciate ligament reconstruction and total arthroplasty (Thienpont 2014). The authors also mentioned other applications of cryotherapy, including first-generation cryotherapy with crushed ice in a plastic bag, cold or gel packs; Second-generation cryotherapy with circulating ice water with or without compression such as Cryo/Cuff (Aircast, Vista, CA, USA) or Game Ready (CoolSystems Inc, Concord, CA, USA); and advanced third-generation computerized devices with continuous controlled cryotherapy (cTreatment, Waegener, Beerse, Belgium; and CTM 5000, Ener-C AG, Baar, Switzerland).

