### **3.7 Risk evaluation (Risk-to-Benefits rationale)**

There is minimal risk for the test subjects during cooling. The test subjects are expressly informed that they can stop the maximum tolerable cooling at any time. This also applies to integrated compression therapy. Furthermore, at least one examiner will be next to the subject during the cooling application in order to stop the intervention in the event of circulatory or other complaints. A fully equipped emergency kit is in the examination room at all times during the examinations. Since the intervention and measurements will take place on the premises of the Regionalspital Surselva AG, [name], first aid can be ordered directly in the event of circulatory and other problems. This information is communicated to the test persons (subject information). The device is used as recommended by the manufacturer.

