#### Securing study participants

The Game Ready applications represent a commonly used cooling and compression intervention in the literature. Nevertheless, the test subjects can discontinue the treatment at any time if they feel unwell. During the cooling applications and measurements, at least one or two examiners will always be next to the test subject in order to discontinue the treatment in case of discomfort. Further precautions are described in chap. 3.7. Risk/Benefits Described.

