## 10.3 Documentation and reporting in Medical Device Category A clinical investigations

Device deficiencies (DD) and all **adverse events (AE)** including all **serious adverse events (SAE)** are collected, fully investigated and documented in the source document and appropriate case report form (CRF) during the entire investigation period, i.e. from patient's informed consent until the last CIPspecific procedure, including a safety follow-up period.

- Documentation of AEs (including SAEs) by the PI includes diagnosis or symptoms, start and stop dates of event, event treatment, event resolution, assessment of seriousness and causal relationship to MD and/or investigation procedure (Art. 32 ClinO-MD, ISO14155).
- Documentation of DDs by the PI includes description of event, start date, investigational device information, action taken with regard to the investigational device, and whether the DD led to an AE. The Sponsor shall review all DDs and determine and document in writing whether they could have led to a SAE (DD with SADE potential) (Art 32. ClinO-MD, ISO14155).

The project works with a CE-certified product. It is a study with 30 or fewer subjects. The study focuses on basic findings. The study aims to gain fundamental knowledge in the field of cryotherapy in combination with compression. The monitoring for quality assurance is carried out by [name], PhD.

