### 10.3.1 Foreseeable adverse events and anticipated adverse device effects

The following foreseeable serious adverse events and product defects may occur:

- tissue damage due to improper or too long use than described by the manufacturer,
- burning, itching, increasing swelling, pain, blisters, increasing redness, discoloration and other visible changes during treatment,
- Change in wound conditions (if the wrap is not applied over the bandage or clothing),
- Risk of electric shock (if other power supplies are used, housing parts are removed, or damaged cables and connecting hoses are used) and
- Device damage (if there is no or too hot water in the ice box, the device is lifted up by the lid, or wraps from other manufacturers have been used).

Participants who complain of ongoing adverse events after graduation/discontinuation of their studies will be contacted by telephone two weeks after graduation and asked about their state of health. If the

undesirable events still exist, the participants will be called up for an additional visit to the Surselva Regional Hospital AG. During this visit, the ongoing events are assessed and documented.

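### Adverse event ascertainment is not equal between the arms from surgery to the Day-4 visit, because only device-arm patients have staffed study sessions and no common check is set

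*Combined protocol and SAP*

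**What the plan says.** **When events are recorded.** Under the test log in section 9.1 the rule is: "Any adverse events must be recorded during each visit". The visits are preoperative, Day 4 and six weeks. They are the same in both arms, although the two tables number them differently. Cooling sessions are a separate row, not a numbered visit.

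**The general duty.** Section 10.3 says that all adverse events "are collected, fully investigated and documented in the source document and appropriate case report form (CRF) during the entire investigation period", from consent to the last procedure and without distinction by arm. It does not say how or how often patients are asked. Section 9.2.4 states that no safety parameters are collected, and 9.2.4.1, on adverse events, holds only a dash.

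**Who is with the patient.** For the device arm, section 3.7 says that "at least one examiner will be next to the subject during the cooling application", and section 8.3 that "at least one research employee will be present during the Game Ready applications and the measurements". Section 8.1.1 adds: "During the cooling applications and measurements, at least one or two examiners will always be next to the test subject". The stated purpose is to stop treatment if the patient is unwell, and 8.3 also uses the presence of staff as the argument for compliance. The time table budgets the sessions as "4x 120 min per day = 480 min per stay". Controls have no corresponding row of study contact. Both arms receive standard physiotherapy, documented by hospital physiotherapists (8.1.1, 8.1.2).

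**Which signs.** Section 10.3.1 lists as foreseeable: "burning, itching, increasing swelling, pain, blisters, increasing redness, discoloration and other visible changes during treatment". Section 3.1 describes the ordinary course: "Recovery after surgery is characterized by pain, swelling, and inflammation in the perioperative tissues".

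**The concern.** How often a postoperative symptom enters the record depends partly on how often someone from the study is there to see it or hear about it. Over the treated days that opportunity differs by arm because of the design. Session staff are also not passive bystanders: the coldest tolerable level is set afresh at each treatment, compression depends on tolerance, and a satisfaction question follows each session. Each of these invites the patient to say how the leg feels, and a complaint made there falls under the duty in 10.3. A control patient with the same complaint on the same day has no study contact at which to raise it.

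Two features make this matter more. Pain and swelling are on the device-event list and are also the expected course after this operation. And under 10.1 and 10.2 a weak relationship that cannot be excluded is enough for an event to count as a device effect. What is at stake is the safety description: with 14 patients per arm, a few extra records change the picture, and the trial's stated aim is to support recommendations.

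**Working it through.** **Inputs.** From the time table in section 9.1: Visit 1, 60 min; sessions, 2 × 60 min per day on 4 days; Day-4 visit, 30 min; six-week visit, 40 min. Group size is 14 per arm (Synopsis, 6.1).

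**Step 1: reproduce the plan's total.** 60 + 8 × 60 + 30 + 40 = 610 min, as the table states. Without the sessions, 610 − 480 = 130 min remain, which is the visit time in either arm. Section 9.3.1 gives 850 min, 240 more, without explanation. The itemised table is used here.

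**Step 2: number of sessions.** The start is given as 48 hours after surgery, yet sessions are to run twice daily over the first four postoperative days. Both statements cannot apply in full by Day 4 and they must be reconciled. Two sessions on each of Days 2, 3 and 4 give six; the budget gives eight. If the Day-4 visit came before that day's sessions, four would precede it.

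**Step 3: study-staff contact after surgery, up to and including the Day-4 visit.**

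| Sessions | Device arm (min) | Control (min) | Ratio of minutes | Occasions |
|---|---|---|---|---|
| 8 | 8 × 60 + 30 = 510 | 30 | 17 | 9 vs 1 |
| 6 | 6 × 60 + 30 = 390 | 30 | 13 | 7 vs 1 |
| 4 | 4 × 60 + 30 = 270 | 30 | 9 | 5 vs 1 |

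After Day 4 each arm has one further visit.

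**Step 4: what this could do to recorded events (illustration only).** Suppose the true rate is the same in both arms, each study contact has the same independent chance p of producing a record, and sessions count as contacts. None of these is given in the documents. Then P(recorded at least once) = 1 − (1 − p)^k, with k = sessions + 2 postoperative visits in the device arm and k = 2 in controls.

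| Assumed p | Device, 8 sessions (k = 10) | Device, 6 sessions (k = 8) | Control (k = 2) | Ratio, 8 sessions | Ratio, 6 sessions |
|---|---|---|---|---|---|
| 0.05 | 40.1% | 33.7% | 9.8% | 4.12 | 3.45 |
| 0.10 | 65.1% | 57.0% | 19.0% | 3.43 | 3.00 |
| 0.50 | 99.9% | 99.6% | 75.0% | 1.33 | 1.33 |

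At p = 0.10 with eight sessions this is about 9.1 against 2.7 of 14 patients with a record. Routine care narrows the gap. If three physiotherapy contacts per patient (also an assumption) captured events equally well in both arms, then k = 13 against 5, giving 1 − 0.9^13 = 74.6% against 1 − 0.9^5 = 41.0%, a ratio of 1.82. The direction is stable under these assumptions; the size is not.

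**Step 5: the two lists of signs.** Pain and swelling stand in both 3.1 and 10.3.1. Redness stands only in 10.3.1; the background names inflammation, not redness. Section 10.3.1 also qualifies swelling and redness as increasing and refers to changes during treatment. The overlap is real for pain and swelling but not complete.

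**The case against.** A good deal can be said for the plan.

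- **No passage says events are sought at sessions.** Staff are there to stop treatment and, by 8.3, to secure compliance. Read literally, the visit rule gives both arms the same recording occasions. This stands: the extra recording is inferred from staff presence together with the duty in 10.3.
- **Section 10.3 covers both arms for the whole period.** Controls are inpatients of the same hospital with documented physiotherapy, so events between visits can reach the record. This stands too, but a duty without a method does not equalise the chance of capture. The data collection form is listed in chapter 17 and is not reproduced, so it cannot be checked for a daily prompt. If it has one for both arms, the point is largely met.
- **The same signs are measured with a control group.** Pain, joint circumference and skin temperature are taken in both arms on Day 4 and at six weeks, by examiners described as blinded (6.2.2). A reader might infer that device effects cannot be told apart from the postoperative course at all. The documents do not support that: the common visits give a comparison, though not for the earlier treated days.
- **Chapter 11 plans no by-arm comparison of adverse events, and 10.2 grades case by case without a control rate.** Correct. The unequal input matters for whatever counts are reported and for which events come up for grading. It is not a fault in the algorithm.

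**Conclusion.** The point holds as one of unequal ascertainment between surgery and the Day-4 visit. Device-arm patients have six to eight staffed hours that controls do not have, no common inquiry is set, and the listed device signs partly coincide with the normal course. Events such as increasing swelling, pain or redness may therefore be recorded more often in the device arm with equal true rates, and are hard to attribute before Day 4.

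A reader might infer 13 to 17 times as many recorded events, or that such events will be recorded mainly in the device arm. Neither follows. The 13- and 17-fold figures compare contact minutes and leave out ward and physiotherapy contact. The 1.3- to 4.1-fold range rests entirely on an assumed chance of detection. The documents do not allow the excess to be estimated.

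The conclusion assumes that staff who notice or hear of an event at a session record it, as 10.3 requires, and that routine care does not already capture events equally in both arms. Efficacy endpoints are not affected. The change is worth making because it is cheap.

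**What to change.** In 9.1, 9.2.4.1 and 10.3, add one identical short check in both arms, at the existing physiotherapy contact, on each hospital day when sessions run (the days follow once the session schedule is reconciled). It should:

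- ask about new or worsening signs from the 10.3.1 list since the previous check, with a simple severity grade. A bare yes/no for pain or swelling would be positive in most patients of both arms and tell nothing;
- be passed to the PI, who keeps responsibility for adverse event documentation and causality.

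In chapter 11, add a sentence that any by-arm adverse event table rests on these checks and the two common postoperative visits. Events noticed only during a cooling session are listed separately, as device-arm observations without a control rate.

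The cost is a short entry on an existing record and slightly more form-filling for the ward physiotherapists. No extra visit or staff is needed, and treatment is unchanged.

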## 9.2 Assessments of outcomes

The following data are collected during all tests described in the sub-protocols in chap. 9.1.

### 9.2.1 Assessment of primary outcome

#### Questionnaire Physical Function [Score]

To determine the subjective assessment of physical function, the KOOS questionnaire is handed out, evaluated and documented. The KOOS questionnaire is highly valid for knee complaints and refers to the subjective impression of the patients (Roos and ToksvigLarsen 2003). The measurement moments take place preoperatively, on the 4th postoperative day and 6 weeks postoperatively.

#### Patient satisfaction [cm]

In order to evaluate the patient satisfaction of the intervention group (Game Ready), the test subjects are asked the question "How satisfied are you with the cooling intervention?" immediately after the intervention. With the help of the Visual Analog Scale, the test subjects rate their satisfaction with a number between 0 (not at all satisfied) and 10 (maximally satisfied). The measurement moments take place twice a day (each time after the cooling intervention) during the hospital stay.

#### Joint circumference [mm]

The joint circumference measurement is carried out by hand with a tape measure. This measurement method showed a high level of reliability. 5cm, 10cm, 15cm above the knee joint space, at the level of the knee joint space, 15cm below the knee joint space, above the lateral malleolus and above the scaphoid bone (Oesch 2007). Both sides are measured. The measurement moments take place preoperatively, on the 4th postoperative day and 6 weeks postoperatively.

#### Range of motion [degrees]

To estimate the range of motion of knee flexion, the "RoMot" app from OT Bioelettronica (Turin, Italy) is used. The patient is in the supine position. The two sensors are applied to the lower and thigh legs. In response to the start command, the test subject tries to bend his knee as much as possible. The heel remains in bed and the longitudinal axis of the leg is also taken into account. Then the other side is measured. The number of degrees indicated by the software on the corresponding tablet is documented. Wireless Bluetooth sensors, for determining the amount of motion, show a high correlation compared to the goniometer measurements, which are currently the most commonly used in practice (Kumar et al. 2015). The measurement moments take place preoperatively, on the 4th postoperative day and 6 weeks postoperatively.

#### Skin temperature [°C]

Skin temperature is also recorded with the help of an infrared thermometer (Voltcraft IR800-20D, Conrad Electronic, Hirschau, Germany). Handheld infrared thermal devices have high measurement accuracy (due to contact-free measurement) and practical handling (Stoop et al. 2020). Skin temperature is measured at four locations of the knee: superolateral, superomedial, inferolateral, and inferomedial

margin of the patella (Zeng et al. 2016). The subject is in a supine position during the measurements. Both sides are measured. The measurement moments take place preoperatively, on the 4th postoperative day and 6 weeks postoperatively.

